### **7.1.3.2 Presence of Anti-FSH Antibodies**

Blood for assessment of the presence of anti-FSH antibodies in the serum will be collected on Day 1 before administration of FE 999049, Day 7 and Day 28. The samples will be analysed under the responsibility of the Department of Bioanalysis at Ferring Pharmaceuticals. Confirmed positive samples will subsequently be analysed for neutralising activity by a validated cell-based neutralising antibody assay.

## **7.2 Other Assessments**

### **7.2.1 FSH Determination Day -3 and Day -1**

FSH for determination of down-regulation will be analysed on Day -3 and Day -1 using a validated standard method at a local laboratory.

### **7.2.2 Serology/Virology**

Determination of hepatitis B surface-antigen, hepatitis C virus antibodies, HIV antibodies and syphilis bacteria are performed at screening for eligibility purposes.

### **7.2.3 Pregnancy Test**

Serum  $\beta$ -human chorionic gonadotropin ( $\beta$ -hCG) will be determined at screening, and Day -1, and at the follow-up visit using validated standard methods. Urine  $\beta$ -hCG will be determined on Day  $-28\pm 1$  and Day  $-10\pm 1$ , prior to administration of DECAPEPTYL Depot 3.75 mg.

### **7.2.4 Gynaecological Examination and Transvaginal Ultrasound**

Gynaecological examination and transvaginal ultrasound will be performed at screening, before dosing (in the period Day -3 to Day -1), and at the follow-up visit. Cytology will be performed at screening if not done within 6 months prior to screening, and at the follow-up visit.

### **7.2.5 Physical Examination**

A complete physical examination will be performed at screening and at the follow-up visit. Information will be recorded for general appearance, central and peripheral nervous system, head and neck (including ears, eyes, nose, mouth and throat), respiratory system, cardiovascular system, gastrointestinal system, lymphatic system, urinary system, musculoskeletal system and skin.

At screening, each category will be evaluated as normal, abnormal not clinically significant or abnormal clinically significant. Abnormal clinically significant findings at screening must be reported on the Medical History Log.

At the follow-up visit, potential changes from screening to the follow-up visit will be evaluated for each category. In case of changes, these will be evaluated as normal, abnormal not clinically significant or abnormal clinically significant. Abnormal clinically significant changes from screening to the follow-up visit must be recorded as adverse events.

### **7.2.6 Drug Screen and Alcohol Breath Test**

To ensure that drugs are not abused, a urine dip stick drug screen and an alcohol breath test will be performed locally at screening and on Day -1. The drug screening will be performed using fresh mid-stream urine for the determination of amphetamines, barbiturates, benzodiazepines, cannabinoids, cocaine, ecstasy, nortriptyline, opiates, phenacyclidine, and methadone.

### **7.3 Handling of Biological Samples**

A detailed description of all sample collections and shipment procedures will be included in a separate laboratory manual. The sponsor or third parties will store the PK and immunogenicity blood samples for a period of up to 2 years after the trial is finalised.

### **7.4 Laboratory Analyses**

All laboratory measurements, except for PK, anti-FSH antibodies and those that are assessed bed-side, will be analysed at a local laboratory. The investigator will review the laboratory results and evaluate and document whether the results are clinically significant or non-significant.

## 8 ADVERSE EVENTS

### 8.1 Adverse Events

#### 8.1.1 Definitions

An adverse event is any untoward medical occurrence in a subject participating in a clinical trial. It includes:

- Any unfavourable and unintended sign, symptom or disease temporally associated with the use of the IMP, whether or not considered to be caused by the IMP.
- Adverse events commonly observed and adverse events anticipated based on the pharmacological effect of the IMP.
- Any laboratory abnormality, vital sign or finding from physical or gynaecological examination assessed as clinically significant by the investigator [note: pre-existing conditions diagnosed through assessments and examinations at the screening visit or during the screening period are not adverse events, but are recorded as medical history].
- Accidental injuries, reasons for any change in medication (drug and/or dose), reasons for any medical, nursing or pharmacy consultation, or reasons for admission to hospital or surgical procedures.
- Overdoses and medication errors with and without clinical consequences.

#### Pre-treatment Adverse Event

A pre-treatment adverse event is any untoward medical occurrence arising or observed between informed consent and administration of the IMP.

#### Treatment Emergent Adverse Event

A treatment emergent adverse event is any adverse event occurring after the administration of the IMP and within the time of residual drug effect, or a pre-treatment adverse event or pre-existing medical condition that worsens in intensity after start of IMP and within the time of residual drug effect.

The time of residual drug effect is the estimated period of time after the administration of the IMP, where the effect of the product is still considered to be present based on pharmacokinetic, pharmacodynamic, or other IMP characteristics. The residual drug effect is generally accepted to be 5 times the terminal half-life. The terminal half-life of FE 999049 after a single administration is expected to be approximately 40-44 hours. Thus, the time from the administration on Day 1 to Visit 13 on Day 11 is likely to cover more than 5 half-lives. All AEs occurring during the treatment and follow-up phase (i.e. including Day 11) are regarded as treatment emergent.

#### Post-treatment Adverse Events

A post-treatment adverse event is any adverse event occurring after the time of residual drug effect of the IMP, i.e. after the visit on Day 11 and until the anti-FSH antibody assessment on Day 28.

## 8.2 Collection and Recording of Adverse Events

### 8.2.1 Collection of Adverse Events

The investigator must monitor the condition of the subject throughout the trial from the time of obtaining informed consent until the end-of-trial visit or end of follow-up period as applicable.

The sources of adverse events cover:

- The subject's response to questions about his/her health (a standard non-leading question such as "How have you been feeling since your last visit?" is asked at each visit).
- Symptoms spontaneously reported by the subject.
- Investigations and examinations where the findings are assessed by the investigator to be clinically significant changes or abnormalities.
- Other information relating to the subject's health becoming known to the investigator (e.g. hospitalisation).

### 8.2.2 Recording of Adverse Events

The investigator must record all adverse events in the Adverse Event Log provided in each subject's -eCRF with information about:

- Adverse event
- Date and time of onset (time can be omitted, if applicable)
- Intensity
- Causal relationship to the IMP
- Action taken to IMP
- Other action taken
- Date and time of outcome (time can be omitted, if applicable)
- Outcome
- Seriousness

Each of the items on the Adverse Event Log are described in detail in the following sections.

#### **Adverse Event**

Adverse events should be recorded as diagnoses, if available. If not, separate signs and symptoms should be recorded. One diagnosis/symptom will be entered per record.

If a subject suffers from the same adverse event more than once and the subject recovers in between the events, the adverse events should be recorded separately. If an adverse event changes in intensity, a worst-case approach should be used when recording the event, i.e. the highest intensity and the longest duration of the event. However, if an adverse event with onset before the first IMP administration (i.e. a pre-treatment adverse event) changes in intensity, this must be recorded as two separate events. The initial adverse event should be recorded with outcome “not yet recovered” and the date and time of outcome is when the intensity changed. The second adverse event should be recorded with date and time of onset when the intensity changed.

*Note:* A procedure is not an adverse event; the reason for conducting the procedure is. Hospitalisation is not an adverse event; the reason for hospitalisation is. Death is not an adverse event, but the cause of death is (an exception is sudden death of unknown cause, which is an adverse event).

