### **Date and Time of Onset**

The date and time of onset is the date and time when the first sign(s) or symptom(s) were first noted. If the adverse event is an abnormal clinically significant laboratory test or outcome of an examination, the onset date and time is the date and time the sample was taken or the examination was performed.

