1.1 Definitions/ Abbreviations

1.1.1 Definition of Terms

Terms	Definitions
Prior medication	Medication taken prior to treatment (i.e. the stop date is before the first IMP administration)
Concomitant medication	Medication that is not stopped before the first IMP administration, or is started between IMP administration and the follow-up visit (visit 13)
Post-treatment medication	Medication with start date after the follow-up visit (visit 13)
Pre-treatment Adverse Event	An Adverse Event with start time after signing of informed consent and before administration of IMP
Treatment Emergent Adverse Event	An Adverse Event that has start time or worsens in intensity after administration of IMP until the follow-up visit (visit 13)
Post-treatment Adverse Event	An Adverse Event that has start time after the follow-up visit (visit 13)
AUC	Area under the concentration-time curve from dosing to infinity
AUC_t	Area under the concentration-time curve from dosing up to time t, where t is the last time point at which the concentration is above the lower limit of quantification.
% Extrap AUC	Percentage of AUC that is due to extrapolation from the last measurable concentration
CL/F	Apparent total systemic clearance
C_{max}	Maximum concentration observed
λ_z	First-order rate constant associated with the terminal (log-linear) portion of the concentration-time curve
NCA	Non-compartmental analysis
t_½	Terminal elimination half-life
t_{max}	Time of maximum observed concentration (C _{max})
V_{z/F}	Apparent volume of distribution associated with the terminal phase

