10.4 Adverse Events

AEs will be coded according to the latest version of the MedDRA. All data will be listed by subject. For treatment emergent AEs, the listings will include the number of days from administration of IMP until the start of the AE. Only treatment emergent AEs (TEAEs) will be presented in summary tables. All summary tables will include columns for each treatment and a total column. Separate data listing will be provided for AEs that are defined as pre-treatment or post-treatment. The following definitions will be used:

- A pre-treatment Adverse Event is an Adverse Event with start time after signing of informed consent and before administration of IMP
- A Treatment Emergent Adverse Event (TEAE) is an Adverse Event that has start time or worsens in intensity after administration of IMP and until the follow-up visit (visit 13)
- A post-treatment Adverse Event is an Adverse Event that has start time after the follow-up visit (visit 13)

If the start date of an AE is completely or partially missing, the AE will be considered treatment emergent unless it can be excluded that it was treatment emergent based on the incomplete date.

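### A pre-treatment adverse event that eases after dosing is counted as treatment-emergent under the SAP definition, in conflict with the protocol's worsening criterion (minor over-counting)

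*Protocol*

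**What the plan says.** Protocol section 8.2.2 (Adverse Event) normally keeps one record per event at its worst intensity. Events that began before dosing are the exception: "i.e. a pre-treatment adverse event) changes in intensity, this must be recorded as two separate events". The first record is closed as unresolved at the time of the change, and for the second: "The second adverse event should be recorded with date and time of onset when the intensity changed". Nothing restricts the split to worsening.

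SAP section 10.4 then defines the summary population: "A Treatment Emergent Adverse Event (TEAE) is an Adverse Event that has start time or worsens in intensity after administration of IMP", with Visit 13 as the end of the window. SAP section 1.1.1 says the same: "An Adverse Event that has start time or worsens in intensity after administration of IMP until the follow-up visit (visit 13". The two conditions are alternatives, and the start-time condition carries no requirement to worsen. Only TEAEs enter the summary tables; pre-treatment events are listed.

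Protocol section 8.1.1 (Treatment Emergent Adverse Event) covers events that occur after dosing and, separately, "a pre-treatment adverse event or pre-existing medical condition that worsens in intensity after start of IMP". It ends with a general sentence: "All AEs occurring during the treatment and follow-up phase (i.e. including Day 11) are regarded as treatment emergent". The same section defines a pre-treatment event as "any untoward medical occurrence arising or observed between informed consent and administration of the IMP".

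**The concern.** Take a subject with a moderate headache at dosing that eases to mild on Day 2. Protocol 8.2.2 creates a mild record with onset on Day 2. The SAP start-time condition makes that record a TEAE, so an improvement is tabulated as an event that emerged after FE 999049.

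Safety and tolerability is one of the two trial objectives, the groups are small and there is no placebo group. Every subject receives two DECAPEPTYL Depot administrations before dosing. Protocol section 1.3 lists headache and abdominal pain among reactions to GnRH agonists, and reports headache and lower abdominal pain among the most frequent events in earlier single-dose FE 999049 trials. A fading run-in symptom could thus appear as a post-dose event of a kind that readers expect from the investigational product.

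**Working it through.** The plan gives no figure to reproduce, so the check is an enumeration of the text.

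**Step 1: which changes are affected.** The intensity scale has 3 grades (protocol 8.2.2, Intensity). An event ongoing at dosing can afterwards be resolved, mild, moderate or severe: 3 × 4 = 12 combinations. Three resolve directly and three keep their grade; none of these six creates a second record. The other six are split:

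| Before dosing → after dosing | TEAE by SAP start-time condition | Meets protocol worsening criterion |
|---|---|---|
| mild → moderate | yes | yes |
| mild → severe | yes | yes |
| moderate → severe | yes | yes |
| moderate → mild | yes | no |
| severe → moderate | yes | no |
| severe → mild | yes | no |

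The texts disagree on three of the six. These are types of change, not frequencies. A mild event has no lower grade and cannot be affected.

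**Step 2: where such a record lands.** The SAP 10.4.1 overview has 10 rows. A non-serious, unrelated stepped-down record enters 3 of them: all TEAEs, non-serious TEAEs, and either moderate or mild TEAEs. Of the 5 tables by system organ class and preferred term in SAP 10.4.2 it enters 3: all, by causality, by intensity. If causality is judged a reasonable possibility, or is missing and so treated as related, it enters 4 of 10 rows and 4 of 5 tables. A record that stays stepped down adds 0 to the Severe row.

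**Step 3: size per subject.** A subject counted solely for this reason adds 1/8 = 12.5 percentage points to a planned dose group and 1/24 = 4.2 points to the total column.

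**Step 4: how often.** The documents give no rate, so none is claimed. Subjects must be healthy (protocol 4.1.1) and pass an eligibility check on Day -1 (protocol section 6, Visit 5). Severe means unable to work or carry on usual activities, which is unlikely in a woman who goes on to be dosed. The realistic case is moderate to mild.

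**Step 5: the proposed rule on test cases.**
- Moderate before dosing, mild on Day 2, unresolved: not higher, so a continuation.
- Mild before dosing, moderate on Day 2: higher, so a TEAE.
- Moderate before dosing, mild on Day 2, severe on Day 5: the second record starts after dosing, so the worst-case recording rule of protocol 8.2.2 carries it as severe; higher, so a TEAE.
- Moderate before dosing, recovered on Day 2, new mild episode later that day with no times recorded: the earlier outcome is recovered, so the new record stays a TEAE.
- Intensity missing before dosing: SAP 10.4.2 would impute severe, which no later grade can exceed, so a true worsening would be lost. The rule keeps such a record as a TEAE.

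**The case against.** The best defence is that the protocol itself supports the SAP's result. Section 8.1.1 never says that a pre-treatment event counts only if it worsens. Its opening words cover any event occurring after dosing, its closing sentence takes in all events through Day 11, and section 8.2.2 makes the second record a separate event with a post-dose onset. Together these give a coherent and conservative convention.

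One reply is that, on this reading, the worsening criterion does nothing for split events, because a worsening also creates a post-dose record. That argument has weight but does not settle the matter. The criterion also covers pre-existing conditions, which section 8.1.1 treats as medical history; they are never split, so it keeps a function.

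Nor is the general onset rule decisive: "The date and time of onset is the date and time when the first sign(s) or symptom(s) were first noted". It suggests that the second record's date is a change date and not a true onset, but section 8.2.2 has a specific rule for split events.

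A reader might therefore infer that the plan produces a plainly wrong TEAE count. The documents do not go that far. They support two classifications of the same record, and the SAP adopts the broader one without addressing the conflict.

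A second fair objection concerns the remedy. Times may be omitted, and a recurrence after recovery is recorded separately, so linking on event and date alone could turn a new same-day episode into a continuation and hide a genuine TEAE. That objection stands, and it is why the rule below also requires an unrecovered outcome on the earlier record.

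**Conclusion.** The conflict is real and minor. As written, the SAP counts an easing moderate or severe pre-treatment event as treatment-emergent, while the protocol names worsening as the criterion for such events and also contains a sentence that can be read more broadly. The error, if it is one, is conservative: extra mild or moderate entries in descriptive tables, with PK unaffected. Both records are listed, and for TEAEs the days from dosing to onset are shown, so a pair can be found by inspection.

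The conclusion rests on reading the worsening criterion as meant to govern split records. It would be wrong to infer that the safety profile is materially distorted or severe events inflated. The 12.5 and 4.2 points are the weight of any one subject, and the number of such subjects cannot be derived from the documents. Priority is low: a small correction to the definitions.

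**What to change.** Leave the splitting rule in protocol 8.2.2 as it is. Add to the TEAE definition in SAP 1.1.1 and 10.4:

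> The second record of a pre-treatment AE split under protocol section 8.2.2 because of an intensity change is a TEAE only if its intensity is higher than that of the last pre-dose record; otherwise it is listed as a continuation of the pre-treatment AE. A record is a continuation only if it is the same event in the same subject, its onset equals the earlier record's outcome date (and time where recorded), and the earlier record's outcome is unrecovered, in either wording used in the protocol. A record that follows a recovered outcome, that cannot be linked, or whose pre-dose intensity is missing stays a TEAE.

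Add to the pre-treatment AE definition in both places that it includes any record classified as its continuation. The phrase on either wording is needed because protocol 8.2.2 (Adverse Event), protocol 9.7.3.4.2 and SAP 10.4.2 say *not yet recovered*, while the outcome list in protocol 8.2.2 has *Not recovered*. Those passages should be reconciled, but the rule does not wait on that.

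SAP section 12 should state that the rule applies the worsening criterion of protocol 8.1.1 to split records and limits that section's general sentence on all events through Day 11.

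The cost is two amended definitions, one note, a small linking derivation and a manual check of the adverse event listing for 24 subjects. The downside is that an event which steps down and then returns only to its pre-dose grade is listed but not counted as a TEAE.

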### **Date and Time of Onset**

The date and time of onset is the date and time when the first sign(s) or symptom(s) were first noted. If the adverse event is an abnormal clinically significant laboratory test or outcome of an examination, the onset date and time is the date and time the sample was taken or the examination was performed.

### **Intensity**

The intensity of an adverse event must be classified using the following 3-point rating scale:

Mild: Awareness of signs or symptoms, but no disruption of usual activity

Moderate: Event sufficient to affect usual activity (disturbing)

Severe: Inability to work or perform usual activities (unacceptable)

### **Causal Relationship to the IMP**

The possibility of whether the IMP caused the AE must be classified as one of the following:

#### Reasonable possibility:

There is evidence or argument to suggest a causal relationship between the IMP and the AE. The AE may occur as part of the pharmacological action of the IMP or may be unpredictable in its occurrence.

Examples:

- AEs that are uncommon but are known to be strongly associated with IMP exposure
- AEs that are not commonly associated with IMP exposure, but the event occurs in association with other factors strongly suggesting causation, such as a strong temporal association or the event recurs on rechallenge with the IMP

### No reasonable possibility:

There is no reasonable evidence or argument to suggest a causal relationship between the IMP and the AE.

Examples:

- Known consequences of the underlying disease or condition under investigation
- AEs common in the trial population, which are also anticipated to occur with some frequency during the course of the trial, regardless of IMP exposure

### **Action Taken to IMP**

The action taken to the IMP in response to an adverse event must be classified as one of the following:

- No change (medication schedule maintained or no action taken)
- Withdrawn
- Interrupted
- Dose reduced
- Dose increased

### **Other Action Taken**

AEs requiring therapy must be treated with recognised standards of medical care to protect the health and well-being of the subject. Appropriate resuscitation equipment and medicines must be available to ensure the best possible treatment of an emergency situation.

If medication is administered to treat the adverse event, this medication should be entered in the Concomitant Medication Log.

### **Date and Time of Outcome**

The date and time the subject recovers or dies.

### **Outcome**

The outcome of an adverse event must be classified as one of the following:

- Recovered (fully recovered or the condition has returned to the level observed at initiation of trial treatment)
- Recovered with sequelae (resulted in persistent or significant disability/incapacity)
- Recovering (the event is improving)
- Not recovered
- Fatal

